5.2 Retesting During Screening or Lead-in Period

Retesting of laboratory parameters and/or other assessments during the Screening or Lead-in period will not be permitted (this does not include parameters that require a confirmatory result).

Any new result will override the previous result (i.e., the most current result prior to Registration) and is the value by which study inclusion will be assessed, as it represents the subject's most current, clinical state.

5.3 Study Materials

The following will be distributed to sites for use in this study:

- Registration Forms
- NCI CTCAE booklets version 3.0
- Elotuzumab Investigator Brochure
- Lenalidomide (Revlimid®) Package Insert
- Drug Preparation Guidelines
- Subject Dosing Diary
- Laboratory Manuals
- CRFs (electronic)
- Pregnancy Surveillance Forms
- Revlimid Risk Management Plan.

5.4 Safety Assessments

All subjects who receive study drug will be evaluated for safety parameters. Additionally, any occurrence of an SAE from the time of consent forward will be documented.

Safety assessment will be performed prior to study drug dosing at dosing visits, unless otherwise specified.

Safety will be evaluated for all treated subjects using the NCI CTCAE version 3.0. Safety assessments will be based on medical review of AE reports and the results of vital sign measurements, physical examinations, and clinical laboratory tests.

Additional procedures and assessments may be performed as part of standard of care however data for these assessments should remain in the subject's medical record and should not be provided to BMS, unless specifically requested by the sponsor. If additional safety assessments are performed for adverse events, then results should be submitted on the CRF.

5.4.1 Vital Signs, Physical Measurements, and Physical Examination

Vital signs (body temperature, respiratory rate, seated blood pressure and heart rate) will be recorded as outlined in [Table 5.1-1](#), [Table 5.1-2](#), and [Table 5.1-3](#). Blood pressure, respiratory rate and heart rate should be measured after the subject has been seated quietly for at least 5 minutes prior to measurement. Subjects in the control arm will have vital signs measured once

at each visit. Subjects randomized to the investigational arm will have additional vital signs as follows:

- Prior to pre-medication administration
- Prior to the start of the elotuzumab infusion
- Thirty minutes after the start of infusion
- At the end of the infusion
- Thirty and 120 minutes post completion of the elotuzumab infusion for Cycle 1 and 2
- Cycle 3 and beyond post infusion vital signs will be measured at 30 minutes
- Subjects who experience a Grade ≥ 2 infusion reaction require vital signs to be monitored every 30 minutes for 2 hours after the end of the elotuzumab infusion.

Height will be recorded at screening. Weight will be measured at study visits as indicated in [Table 5.1-1](#), [Table 5.1-2](#), and [Table 5.1-3](#).

A full physical examination will be performed at the screening visit, whereas a targeted exam will occur at Day 1 and during on-treatment up to 3 days prior to dosing and post-treatment visits. A targeted physical examination may be performed by a qualified professional guided by the examiner's observations and/or subject complaints on new or changed conditions, symptoms, or concerns. Targeted physical exam includes assessment of heart, lung, and abdomen.

5.4.2 Performance Status

Performance assessment will be performed at Screening, on-treatment Day 1 of each cycle and at End of Treatment visit using ECOG performance scale and criteria as described in [Appendix 2](#). The assessment should be completed prior to any study-related procedures, treatment or clinician assessment.

5.4.3 Echocardiogram or MUGA scan and Electrocardiogram

A MUGA scan or 2-dimensional echocardiogram and electrocardiogram (ECG) will be performed at screening within 28 days of randomization.

5.4.4 Laboratory Assessments for Safety

All safety laboratory assessments indicated in [Table 5.4.4-1](#) should be done at a local laboratory.

Table 5.4.4-1: Safety Laboratory Assessments (may be drawn up to three days prior to visit)

	Screening as outlined in Table 5.1-1 within 14 days of randomization	Study Visits as outlined in Table 5.1-2 and Table 5.1-3
Hematology		
CBC	X	X
Differential	X	X
Platelets	X	X
Chemistry		
Sodium	X	X
Potassium	X	X
Chloride	X	X
Carbon Dioxide or Bicarbonate ^a	X	X
Albumin	X	X
Alkaline Phosphatase	X	X
ALT (SGPT)	X	X
AST (SGOT)	X	X
Total Bilirubin	X	X
Direct Bilirubin (if total bilirubin is abnormal)	X	X
Lactate Dehydrogenase	X	X
BUN (or Urea)	X	X
Creatinine and Creatinine Clearance ^b	X	X
Glucose	X	X
Calcium	X	X
Total Protein	X	X
Coagulation Test		
PT	X	X ^c
PTT	X	
INR	X	X ^c
Pregnancy Test		
Urine or Serum Pregnancy	X (2 tests: one 10 - 14 days prior to the start of study drug and one within 24 hours prior to the start of study drug)	X

Table 5.4.4-1: Safety Laboratory Assessments (may be drawn up to three days prior to visit)

	Screening as outlined in Table 5.1-1 within 14 days of randomization	Study Visits as outlined in Table 5.1-2 and Table 5.1-3
Urinalysis		
Protein	X	
Glucose	X	
Urobilinogen	X	

^a To be done in sites where this is a standard part of the chemistry panel. In sites where testing for CO₂/HCO₃ is not standard, the test is optional.

^b To be measured by 24-hour urine collection or estimated by the Cockcroft and Gault formula in sites.

^c To be done if subject is being treated with warfarin for thromboembolic prophylaxis. Subjects who are not on vitamin K antagonists do not require coagulation tests after screening

5.5 Efficacy Assessments

Efficacy endpoints will be based on serum and urine protein electrophoresis (SPEP and UPEP), corrected calcium (serum calcium and serum albumin), and bone marrow assessments at predefined intervals as specified in [Table 5.1-1](#), [Table 5.1-2](#), and [Table 5.1-3](#). Assessments for SPEP and UPEP will be based on central lab results, whereas assessments of bone marrow, bone lesions, extramedullary plasmacytomas, and corrected calcium will be based on local analysis at the site. Serum β 2 microglobulin will be performed locally at screening. If SPEP and UPEP M protein are performed at a local laboratory, results must be recorded in the CRF/eCRF.

5.5.1 Primary and Secondary Efficacy Assessment

Response assessments according to the international diagnostic criteria of the International Myeloma Working Group (IMWG criteria)²¹ will be used for the primary analysis. For the purposes of this study, all subjects' tumor assessments by SPEP M protein and UPEP M protein quantification, corrected calcium (calcium and albumin), and serum free light chain (when indicated for CR assessment), should be re-evaluated per the protocol-stated frequency relative to the date of first dose of study drug until disease progression based on the IMWG criteria, irrespective of dose delays or treatment cycle. **If subject does not have documented disease progression at time of study drug discontinuation, then tumor assessments should still be performed according to the same schedule described above until disease progression even if a subsequent anti-myeloma treatment is initiated prior to disease progression.**

All efficacy laboratory assessments should be done through the central laboratory, except corrected calcium, and bone marrow assessments for plasma cell percentage and light chain restriction (clonality by Immunohistochemistry or flow cytometry). All bone marrow aspirate and core biopsy samples should be assessed locally. For any SPEP or UPEP assessment performed locally, in lieu of a central lab assessment, (ie, if the subject cannot complete a visit at

the study site), M protein quantification must be performed. Any laboratory samples analyzed locally, including for efficacy, must be entered on the appropriate CRF.

5.5.2 **Laboratory Assessments for Myeloma**

All serum and urine lab tests must be sent to the central lab, except serum calcium and albumin which are performed locally, until disease progression or withdrawal of consent, even if the subject is discontinued from study therapy and has started new myeloma therapy.

Twenty-four-hour urine sample can be collected within ± 7 days of visit, and must be obtained with each cycle in all subjects who have measurable UPEP M protein (≥ 200 mg/24 hours) at baseline. Subjects who have urine M protein of < 200 mg/24 hours at baseline and at next 2 subsequent assessments do not have to submit q4 week urine samples with each cycle (but must submit q12 week urine samples) until SPEP M protein values becomes undetectable. In order to full fill CR/sCR criteria, both serum and urine immunofixation must be performed and be negative on two consecutive assessment. Therefore, at the time SPEP becomes undetectable, 24-hr UPEP collection should promptly resume and continue q4 weeks until SPEP becomes detectable. Any local serum and urine myeloma lab tests that may also have been performed must also be reported in the CRF.

- 1) **Serum:** serum protein electrophoresis (SPEP) for M protein quantification, total serum protein, immunofixation, and quantitative immunoglobulin assay.
 - a) **Immunofixation:** Immunofixation of serum is required at baseline and to confirm CR regardless of whether measurable M-protein was present at baseline.
 - b) **Serum free light chain:** Serum should be collected at screening and time of CR for serum free light chain analysis. This measurement is required to document sCR.
 - c) **Other:** All other serum tests will be followed at each tumor assessment.
- 2) **Urine:** 24-hour urine collection electrophoresis for M protein quantification, urinary light chains, and immunofixation. 24-hour urine must be collected with each cycle for all subjects, except for those subjects with no measurable M protein in the urine at baseline and at next two subsequent time points.
 - a) Immunofixation of urine is required at baseline and to confirm CR regardless of whether measurable M-protein was present at baseline.
 - b) All other urine tests will be followed at each tumor assessment.
- 3) **Bone marrow aspiration/biopsy:** Assessment of bone marrow for percentage plasma cells is required within 28 days of randomization and while on study to confirm CR (ie, subjects who become immunofixation negative) or, if clinically indicated, at time of suspected disease progression (a second confirmation bone marrow analysis for CR is not needed). The percentage CD138⁺ cells and clonality (based on kappa/lambda ratio) will also be assessed to confirm stringent CR (sCR). Flow cytometry will be performed only to confirm CR. In addition, biomarker tests must also be performed on the fresh bone marrow sample obtained at screening (if applicable; refer to [Section 5.7.2](#)).

Table 5.5.2-1: Bone marrow samples

Bone marrow sample	Local Laboratory	Local Central Laboratory
Aspirate ^a	
Samples required at the following times to evaluate percentage plasma cells:
 
 • Screening (within 28 days of randomization) • When subject is immunofixation negative in both serum and urine (second bone marrow sample not required for confirmation) 
In addition, evaluate flow cytometry to assess plasma cell clonality (i.e., lambda and kappa IHC or flow cytometry to assess light chain restriction).
 
 • At time of suspected disease progression, if needed (see Section 5.5.4) to assess progression in subjects who's myeloma become nonsecretory 	
Screening (within 28 days of randomization)
 
 • send for genetic assessments (karyotype and FISH)^b
Biopsy	
Not required by protocol unless an aspirate sample (at any time point above) is not available due to a dry tap or due to laboratory preferences of the local pathologist. IHC of biopsy for clonality by local lab if aspirate is not available.
	

^a Should be replaced by core biopsy sample only if: 1) aspirate is not available at any time point due to a dry tap or 2) subject is immunofixation negative in serum and urine and flow cytometry is not available at the site.

^b Genetic assessments (karyotype and FISH) should be performed at the local central laboratory designated by the Sponsor on a fresh bone marrow sample. However, if a new bone marrow sample collection is not feasible and if this assessment was performed locally within the 28 days of randomization, the local results must be entered into the eCRF.

4) **Serum corrected calcium:** Serum corrected calcium should be collected with each cycle for all subjects until disease progression.

5.5.3 **Imaging Assessments for Myeloma**

5.5.3.1 **Skeletal Survey**

Skeletal survey, by conventional radiography, for metastatic disease will be performed at screening (within 28 days prior of randomization), and on study if clinically indicated (development of compression fracture does not exclude response). Use of conventional or low dose CT scan (ie, of the spine) or MRI bone survey is acceptable. If imaging is performed on treatment for assessment of progression, the site must use the same modality of imaging as used in screening. The number and location of skeletal lesions and whether they are lytic should be

recorded on the eCRF. On treatment survey should record whether there is an increase in the number or size of lytic lesions.

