3.3.1 Inclusion Criteria

1. Signed Written Informed Consent

- a) Subject is, in the investigator's opinion, willing and able to comply with the protocol requirements.
- b) Subject has given voluntary written informed consent before performance of any study related procedure not part of normal medical care, with the understanding that consent may be withdrawn by the subject at any time without prejudice to their future medical care.

2. Target Population

- a) Eastern Cooperative Oncology Group (ECOG) performance status ≤ 2 .
- b) Life-expectancy > 3 months.
- c) Newly diagnosed, untreated, symptomatic, documented myeloma AND;
 - i) Who are not candidates for high-dose therapy plus SCT because of age (≥ 65 years) or coexisting conditions. Refusal to undergo high dose therapy with SCT is **NOT** sufficient for entry onto CA204116 for a subject < 65 years old. There must be a comorbidity that prevents SCT for a subject < 65 years old, AND;
 - ii) Measureable disease (patient must meet one of these criteria)
 - (a) serum IgG M-protein ≥ 0.5 g/dL OR
 - (b) serum IgA M-protein ≥ 0.5 g/dL OR
 - (c) serum IgM M-protein ≥ 0.5 g/dL OR
 - (d) Urine M-protein ≥ 200 mg/24-hour OR
 - (e) Serum free light chain (sFLC) assay showing involved FLC level ≥ 10 mg/dL (≥ 100 mg/l) provided the serum FLC ratio is abnormal
- d) Subject Re-enrollment: This study does not permit the re-enrollment of a subject that has discontinued the study as a pre-treatment failure.

3. Age and Reproductive Status

- a) Males and Females, ages ≥ 20 years, inclusive
- b) Subjects must be willing to refrain from blood donations during study drug therapy and for 90 days after therapy.
- c) Women of childbearing potential (WOCBP) and men must be using 2 acceptable methods of contraception to avoid pregnancy throughout the study for a period of at least 1 month (4 weeks) before study treatment and women for up to 120 days, men for up to 180 days after the last dose of study drug in such a manner that the risk of pregnancy is minimized. See [Section 3.3.3](#) for the definition of WOCBP and also refer to the Revlimid risk management plan guidelines.

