Myeloma Urine and Serum Lab Tests	Every 4 weeks from date of first dose of study drug until progression, regardless of whether patient is on study therapy or subsequent therapy.					
Day 1 of each cycle (except Cycle 1 - refer to Screening visit for defined window) until disease progression.
 
24-hour urine sample can be collected within ± 7 days of visit, and must be obtained with each cycle in all subjects who have measurable UPEP M protein (≥ 200 mg/24 hours) at baseline.
 
Subjects without measurable urine M protein at baseline and at next two subsequent cycles do not have to submit q4 week urine samples with each cycle (but must submit q12 week urine samples) until SPEP M protein becomes undetectable. In order to full fill CR/sCR criteria, both serum and urine immunofixation must be performed and be negative on two consecutive assessment. Therefore, at the time SPEP becomes undetectable, UPEP sample collection must promptly resume for these subjects, and also continue q4 weeks until SPEP becomes detectable.
 
Central lab analysis. (Section 5.5.2)

Bone Marrow Aspiration/Biopsy	For confirmation of CR/sCR if applicable or, if clinically indicated at time of suspected disease progression					Bone marrow aspirate is mandatory. Bone marrow biopsy is optional. Bone marrow samples must be assessed for clonal cells at the local lab by immunohistochemistry of the biopsy or immunofluorescence (flow cytometry) of the aspirate. Plasma cell percentage and light chain restriction assessments are required. (Section 5.5.2)
Skeletal Survey	If clinically indicated					Section 5.5.3.1
CT/MRI assessment for extramedullary soft tissue plasmacytoma	As clinically indicated and at the time of CR/sCR assessments					Section 5.5.3.2

Table 5.1-2: Short-term Procedural Outline (CA204116) Cycles 1 & 2

Procedure	Day 1	Day 8	Day 15	Day 22	Rest Days 23 - 28 ^a	Notes
Response per IMWG based criteria	Every 4 weeks from date of first dose of study drug until progression, regardless of whether patient is on study therapy or subsequent therapy.					Investigator assessment All response categories require two consecutive assessments. (Section 5.5.4)
Serum PK (Investigational arm only)	←————→					Refer to Section 5.6 for specific time points
Anti-Drug Antibody (ADA) (Investigational arm only)	←————→					Refer to Section 5.6 for specific time points
██████████	←————→					Refer to Section 5.7.1 for specific time points
Study Drug						

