5.5.4 Definitions of Response Based on IMWG

See Table 5.5.4-1 and Table 5.5.4-2 for definitions of response and progression. All criteria are derived from IMWG.²¹ All response categories require 2 consecutive assessments. The second of the 2 consecutive assessments should occur at the next planned tumor assessment (every 4 weeks after the first dose).

Table 5.5.4-1: IMWG Criteria for Response

Category	Criteria ^a
Stringent Complete response (sCR)	CR as defined below plus Normal serum free light chain (FLC) ratio and Absence of clonal cells in bone marrow ^b by immunohistochemistry or immunofluorescence. ^c
Complete response (CR)	The first two bullet points must be met. The remaining bullet points must be met only as indicated. Negative immunofixation on both serum and urine and, Bone marrow aspirate ^b containing < 5% plasma cells, No increase in size or number of lytic lesions should occur (development of a compression fracture does not exclude response) with disappearance of soft tissue plasmacytomas, Skeletal survey must be performed ONLY if clinically indicated.
Very Good partial Response (VGPR)	Serum and urine M-protein detectable by immunofixation but not on electrophoresis or 90% or greater reduction in serum M-protein plus urine M-protein < 100 mg per 24h. If the serum and urine M-protein are unmeasurable, a ≥ 90% decrease in the difference between involved and uninvolved FLC levels is required in place of M-protein criteria.
Partial response (PR)	All of the following conditions must be met for PR: Greater than or equal to 50% reduction in serum M-protein and Reduction of ≥ 90% in urinary M-protein or a decrease to < 200 mg/24 hours, If the serum and urine M-protein are unmeasurable, a ≥ 50% decrease in the difference between involved and uninvolved FLC levels is required in place of M-protein criteria. Greater than or equal to 50% reduction in the size of soft tissue plasmacytomas present at baseline, No increase in size or number of lytic bone lesions (development of a compression fracture does not exclude response). Skeletal survey must be performed ONLY if clinically indicated to confirm that lytic lesions have not increased and that no new lesions are seen; if done, this should occur at the 4-week confirmatory time point following initial determination of PR.

Table 5.5.4-1: IMWG Criteria for Response

Category	Criteria ^a
Stable disease (SD)	Not meeting criteria for CR, VGPR, PR or progressive disease.

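### Serum free light chain is scheduled only at screening and at CR, yet subjects measurable by FLC alone are eligible and need serial FLC for PR, VGPR and FLC-route progression

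*Protocol*

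**What the plan says.** **Sampling.** Protocol 5.5.2 item 1(b): "Serum should be collected at screening and time of CR for serum free light chain analysis". The purpose given there is documentation of sCR. Item 1(c) then continues: "All other serum tests will be followed at each tumor assessment". Section 5.5.1, listing what is re-evaluated at each assessment, includes FLC only in the qualified form "serum free light chain (when indicated for CR assessment". Section 5.5 opens with "Efficacy endpoints will be based on serum and urine protein electrophoresis (SPEP and UPEP), corrected calcium", adds bone marrow, and does not mention FLC. The 4-weekly myeloma laboratory rows of Tables 5.1-2 and 5.1-3 do not itemise the tests and refer back to 5.5.2.

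**Eligibility.** Protocol 3.3.1 criterion 2c(ii) is met by any one of five measures. The fifth, (e), begins "Serum free light chain (sFLC) assay showing involved FLC level". SAP 7.2.2 treats the same measure as sufficient for measurable disease.

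**Endpoints.**
- Table 5.5.4-1: when serum and urine M-protein are unmeasurable, a "decrease in the difference between involved and uninvolved FLC levels is required in place of M-protein criteria". The fall must be at least 50% for PR and at least 90% for VGPR, and 5.5.4 asks for two consecutive assessments.
- Table 5.5.4-2: for the same subjects there is a progression route through a confirmed FLC rise of at least 25%, more than 10 mg/dL in absolute terms, measured from nadir.
- Table 5.1-2: the row "Response per IMWG based criteria" falls due every 4 weeks.
- SAP 4.1.2.1: in these subjects an adequate tumor assessment needs an FLC result.
- SAP 7.5: ORR and PFS are analyzed on all randomized subjects.

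**The concern.** The sampling text and the endpoint text cannot both be followed for a subject who qualified on FLC alone. The response table makes FLC the substitute for M-protein, while the laboratory section collects FLC on study only when CR is being documented. A fall confirmed at two consecutive 4-weekly visits cannot be shown from one sample at screening and one at CR, and a nadir cannot be found without serial values.

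Two endpoints are exposed.

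- **ORR.** An FLC-only subject in PR or VGPR who never reaches CR has no documented response and counts as a non-responder. That biases ORR downward and costs power in the primary test.
- **PFS.** Without on-study FLC the subject has no adequate post-baseline assessment. If event-free, the subject is censored at randomization under the primary definition (SAP 4.1.2.3). The ITT definition (SAP 4.1.2.4) also censors at the last adequate assessment, so it has no on-study date to use either.

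**Working it through.** **1. Text check, FLC-only subject, FLC sampled as scheduled**

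| Classification | What it needs | Available? |
|---|---|---|
| PR | FLC difference down ≥ 50%, two consecutive assessments | No |
| VGPR | FLC difference down ≥ 90%, two consecutive assessments | No |
| CR | Negative serum and urine immunofixation, marrow < 5% plasma cells | Yes |
| sCR | CR plus normal FLC ratio and no clonal cells | Yes, FLC is drawn at CR |
| PD by FLC | Confirmed rise from nadir | No |
| PD by serum paraprotein, urinary light chain, marrow, bone, plasmacytoma or calcium | Non-FLC data | Yes |
| Adequate visit (SAP 4.1.2.1) | FLC result | No, except at CR |

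**2. The plan's own figures** (Protocol 8.1, SAP 5: 32 or more of 40, null 71%, alternative 85%, one-sided 15%, power 80%)

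- Exact alpha = P(Bin(40, 0.71) ≥ 32) = 0.139. A cut-off of 31 would give 0.236, so 32 is the correct cut-off for a 15% level.
- Exact power = P(Bin(40, 0.85) ≥ 32) = 0.865, which meets the stated 80%.

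**3. Effect of unscorable FLC-only subjects**

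Assumptions, none of which the documents supply: m FLC-only subjects among the 40 on ELd; each is scored as a responder with probability p; the other 40 − m respond at 85%.

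Power = Σ over j = 0..m of Bin(j; m, p) × P(Bin(40 − m, 0.85) ≥ 32 − j)

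Example, m = 1: P(Bin(39, 0.85) ≥ 31) = 0.8799 and P(Bin(39, 0.85) ≥ 32) = 0.7777. With p = 0.30, power = 0.30 × 0.8799 + 0.70 × 0.7777 = 0.808.

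| Scenario | p | m = 0 | 1 | 2 | 3 | 4 |
|---|---|---|---|---|---|---|
| No CR, no unscheduled FLC | 0 | 86.5% | 77.8% | 65.9% | 51.3% | 35.5% |
| 30% reach CR, no unscheduled FLC | 0.30 | 86.5% | 80.8% | 73.9% | 65.7% | 56.6% |
| Each has a 50% chance of unscheduled FLC (then responds at 85%), otherwise never CR | 0.5 × 0.85 = 0.425 | 86.5% | 82.1% | 77.0% | 71.1% | 64.6% |
| FLC drawn in all, respond at 85% | 0.85 | 86.5% | 86.5% | 86.5% | 86.5% | 86.5% |

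In the first row, expected ORR is 0.85 × (40 − m)/40: 82.9%, 80.8%, 78.6% and 76.5% for m = 1 to 4.

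**4. PFS**

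With no event and no on-study FLC, both definitions leave only the randomization date. Events are also at risk under the primary definition. Its opening sentence in SAP 4.1.2.3 counts progression or death only within 10 weeks of the last adequate assessment, so a later marrow, bone or calcium progression, or a death, could also be dropped. The second censoring rule there measures the 10 weeks from the last tumor assessment without that qualifier, so the outcome depends on which wording is applied. The ITT definition keeps such events.

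**The case against.** The case on the other side has several parts.

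- **Nothing forbids extra FLC.** Item 1(b) sets collection times without excluding others. Response is due every 4 weeks under criteria that call for FLC, so a site applying them has reason to request it. Investigators assign best response (SAP 7.1), local results are captured ("Any local serum and urine myeloma lab tests that may also have been performed must also be reported in the CRF"), and SAP 7.5.4 already lists FLC values by subject. This stands as a reason why the loss is conditional. It does not remove the conflict: a rule that results be reported if obtained does not require that they be obtained.
- **The list in 5.5 is weak evidence.** It also omits immunofixation, which CR requires, so it is not exhaustive. Accepted; the case rests on items 1(b) and 1(c) and the qualifier in 5.5.1.
- **The subgroup may be tiny.** FLC-only subjects are those who fail every serum and urine M-protein threshold, and non-secretory myeloma is excluded. With one such subject, power is still 77.8% to 82.1%, about the planned 80%. The 35.5% figure needs four such subjects, no CR and no unscheduled FLC. This stands, and the larger losses should be read as a bound.
- **Material not seen.** Some rows of Table 5.1-3 and the laboratory manual are unavailable. The surviving myeloma laboratory row of that table matches Table 5.1-2 and points back to 5.5.2. A manual that added serial FLC would still disagree with 5.5.1 and 5.5.2.

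**Conclusion.** The concern holds. The eligibility, response, progression and adequate-assessment rules need serial FLC in FLC-only subjects, and the sampling text does not provide it. No visible passage reconciles them. Confidence in the textual conflict is high.

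The numerical effect is conditional on how many FLC-only subjects were randomized to ELd, how many reach CR, and how often sites draw FLC unprompted. None of these is in the documents. Zero such subjects, or FLC drawn in all of them, means no loss. One leaves power near the planned 80%. Two bring it below 80% in each of the three scenarios with incomplete FLC (65.9% to 77.0%). The direction is against ELd in the primary test, and event-free PFS follow-up in these subjects is lost under both definitions. This should be fixed: it touches the primary endpoint and is cheap to correct.

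**What to change.** - **Protocol 5.5.1, 5.5.2 item 1(b), Tables 5.1-2 and 5.1-3:** require central-laboratory serum FLC at every 4-week assessment until progression for subjects without measurable serum and urine M-protein at baseline. Keep the existing screening and CR samples for everyone.
- **Protocol 5.5:** add FLC, for these subjects, to the tests on which efficacy endpoints rest.
- **SAP, visits already past:** state that any recorded central or local FLC result will be used, and report the number of FLC-only subjects by arm. The light chain disease category in SAP 7.3.3 is not the same group.
- **SAP, any sensitivity analysis:** define the group by baseline measurability, not by missing on-study FLC, which would select on a post-randomization outcome.
- **SAP 4.1.2.3:** make the 10-week rule refer consistently either to the last adequate assessment or to the last assessment.

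The cost is one added assay per visit in a small subgroup, on serum already shipped every 4 weeks, plus wording changes. No new procedure for the subject is involved.
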